APPLICATION FORM FOR THE RESEARCH PROTOCOL

Date: 15/07/2023

Número del estudio: REST-ECL-2023-08

Versión del protocolo: 2.0.

Fecha de la versión: 10/10/2023

Fecha de presentación: 15/07/2023

Investigador/a Principal: [name]

Investigador/a Secundario/a: [name], [name], [name]

Tutor/a / Monitor/a: [name]

Departamento: Odontología Restauradora y estética

Línea de investigación: Investigación básica y aplicada en odontología

Título de la investigación: "Clinical and anatomical factors influencing accuracy in fully guided implant placement"

1. Introduction.

Digital technologies have been widely used in current implant dentistry practice improving clinical outcomes. Computer-guided surgery (CGS) has been introduced to transfer the planned implant position from specific planning software to a surgical procedure. Therefore, implant placement using CSG provides better outcomes regarding the **3-Dimensional (3D)** implant position than free-hand implant placement, shorter surgical time, less discomfort to the patient, and allows prosthetically driven implant placement.¹

Nowadays, static system surgery has been more often applied in clinical practice than dynamic systems. The literature has reported that there exist cumulative sums of errors throughout the guided implant surgery sequence, for example improper

guide positioning. Mucosal thickness and mobility can be a variable that might affect the final position of the guide; therefore, the outcome of the implant position can be influenced as well.^{2,3}

Studies regarding the accuracy of implant placement with CGS have reported that there can be a deviation between planned and placed implant position. A recent systematic review has demonstrated that the total mean deviation of 1.2 mm (1.04–1.44 mm) at the implant platform level and 1.4 mm (1.28–1.58 mm) at the implant apex level was found in the case of implant placement with CGS.³

Several reports revealed that some clinical factors such as the surgical technique, guide type, and implant position can affect the accuracy of the implant placement with CGS.^{3,4}

Moreover, the impact of the jawbone condition, such as bone quantity and quality in the implant placement site, affecting the accuracy of implant placement with CGS remains unclear.^{4,5}

Putra et al.⁶ reports that with low bone density, the drilling trajectory might deviate toward the softer part of the bone after the second drilling procedure. Therefore, highest deviation was found in the cases that the bone density was less than 500 Hounsfield unit (HU).

Multiple bone condition predictors like bone density, bone width, and cortical bone thickness significantly influenced the accuracy in implant placement with CGS.

Some other factors like implant site, type of implant (immediate, early or delay), mucosal thickness, graft in the area, quantity of implants have been reported as a factor influencing the accuracy of the guided surgery.^{6,7}

The aim of this cohort prospective study is to assess the influence of clinical and anatomical factors on the accuracy of computer-guided surgery. The following factors will be taken into consideration for the analysis of the data: 1) Implant location (anterior or posterior); 2) Single or multiple implants; 3) Mucosal thickness; 4) Native or regenerated bone, 5) immediate or delay implant.

2. Objectives.

Overall objective.

The aim of this cohort prospective study is to assess the influence of clinical and anatomical factors on the accuracy of computer-guided implant surgery on immediate and delayed implant placement:

Specific objectives:

- 1) To assess the influence of implant location (anterior or posterior) on the accuracy of CGS
- 2) To assess the influence of time for implant placement (immediate or delay) on the accuracy of CGS.
- 3) To assess the influence of type of bone (native or regenerated bone)
- 4) To assess the influence of bone density on the accuracy of CGS.

Hypothesis.

- 1: H1 implant location (anterior or posterior) has an influence on the accuracy of CGS
- 2: H1 The time for implant placement (immediate or delay) has an influence on the accuracy of CGS.
- 3: H0 The mucosal thickness does not have an influence on accuracy of CGS.
- 4: H1 The bone density has an influence on the accuracy of CGS.

Material and methods.

The study will be performed at a private practice (Blasi Dental Clinic) which is under the tutelage of the Universitat Internacional de Catalunya (UIC) CElm.

Moreover, the present study will be registered in clinicaltrials.gov.

For the sample size calculation, we use as reference Putra's¹⁴ article where it is reported correlations between different deflection parameters and bone density. These are weak-moderate magnitude correlations (0.3<r<0.5).

The sample size was calculated for 3 levels of statistical power, a 95% confidence level with Pearson's linear correlation coefficient null test)

Degree of correlation Power reached

	70%	80%	90%
r=0.3 (weak)	67	84	112
r=0.5 (moderate)	23	29	37

To detect a weak magnitude correlation as significant, 84 patients will be needed for this study.

Inclusion criteria.

- Patients between 25 to 60 years old.
- Periodontally stable patients. Adequate oral hygiene with less than 15% Full Mouth Plaque Score (FMPS).
- Patients who need dental implant treatment without simultaneous regeneration.
- Ability to follow instructions and availability to attend for regular compliance during the entire study.
- With presence of partial edentulism (at least 6 remaining teeth distributed in the dental arch to support the guide).

Exclusion criteria:

- Active infections

- Untreated periodontal disease
- Heavy smokers (>10 cigarettes per day)
- Drug / Alcohol dependency
- Medical condition contraindicating implants dependency
- Patients under bisphosphonate therapy
- Limited mouth opening

All the information will be given to the patients before sign and obtain the informed consent form.

Clinical procedures.

After assessing the fulfillment of the inclusion criteria, pre-operative cone beam computed tomography (CBCT) (Newtom, Cefla S.C.) and intraoral digital impressions (Trios®, 3Shape Dental Systems, Denmark) will be obtained for each patient to achieve a digital wax-up and a presurgical plan for the exact position of the implants by a single calibrated operator (RP).

Every patient could have a maximum of four implants to be placed (one per quadrant), in those cases, there will be one guide per implant.

The digital imaging and communications in medicine (DICOM) files will be imported to a guided-surgery planning software (Codiagnostix, Dental wings) to perform an implant planning based on the digital wax up; in this step the assessment of the mucosal thickness will be performed using the STL and the DICOM files superimposed. The measurement will be taken from the crestal bone until the soft tissue surface (mm).

Furthermore, a surgical guide will be designed, and 3D printed (SprintRay Pro S; SprintRay Inc) with implant guide resin (SprintRay EU Surgical Guide Clear; SprintRay Inc) by RP for the surgical procedure, supported by the whole dental arch, and reinforced with one bar across the arch.

Through guided surgery, previously planned and designed based on CBCT study and CAD/CAM scanning, placement of Conelog Progressive line implants

(Biohorizons Camlog, Iberia) will be performed in maxilla or mandibula in a one stage surgery by a 8 years' experience operator (GB).

Implant placement will be fully guided and a postoperative CBCT in ECO mode ($35\mu\text{Sv}$) will be taken after the implant placement to assess the final position.

Both CBCT will be aligned (pre-op scan and post-op scan) to make calculations by a single evaluator (AB) included the following (Fig. 1): (1) angle: angle deviation measured in degrees; (2) base: deviation at implant shoulder in millimeters; (3) tip: deviation at implant apex in millimeters; (4) 3D offset: global deviation in 3D directions in millimeters; (5) mesiodistal deviation in millimeters: (+) deviated to the distal direction and (-) deviated to the mesial direction; (6) buccolingual deviation in millimeters: direction: (+) deviated to lingual direction and (-) deviated to buccal direction; and (7) apicocoronal deviation in millimeters: direction: (+) deviated in the apical direction. and (-) deviated in the coronal direction.

[figure not shown]

Figure 1. Parameters to evaluate de position of the implant. ¹⁴

Clinical and study schedule

The estimated appointments for all patients:

- Screening visit: Selection, recruitment of patients, and signing of informed consent.
- First visit: Data collection (intraoral scanning and CBCT acquiring).
- Second visit: Implant placement and post-operative CBCT.

Ethics

This protocol follows the ethical principles regarding human experimentation recommended by the World Medical Association in the Declaration of Helsinki.

After fulfilling the inclusion criteria, all patients will receive a full informed consent.

After evaluation and clarification of possible concerns, the patient will return the signed consent as an agreement of participation.

Statistical analysis.

A descriptive analysis will perform by analyzing the mean, standard deviation, minimum, maximum values, and median for each outcome. For a 95% confidence level and an estimated standard deviation, T-test and Pearson's linear correlation coefficient null test will be used to analyze the data.

Study limitations

This clinical study presents some limitations to be taken into considerations. First, if the surgical guide could not fit properly, present movements or break during the procedures, Second, the need of taking two CBCT in one month can represent a topic to be aware. And finally, the data should permit the correct alignment for further analysis and evaluation and its quality must be enough to facilitate the data analysis.

Contingency plan.

Rewarding the mishap of the fitting of the guide, in those cases we will print two guides per case, to have a backup if the first guide breaks. If the guides are not fitting properly, the patient should be excluded from the study.

[figure not shown]
For this study we will use the ECO mode which only presents a minimum effective dose of 9 μ Sv (four times less radiation than a regular CBCT and almost the same radiation as an orthopantomography)

Moreover, if any of the data collected presents any error that could interfere in the data analysis, the patient will be excluded for the study.

Annexes

- a. Flow chart
- b. Patient data collection
- c. Timeline

a. Flow chart

b. Data collection

PATIENT DATA COLLECTION	
PATIENTS PRE-SURGICAL INFORMATION	
Patient number: _____	
Age: _____	
Sex: _____	
Medical conditions _____	
Allergies: _____	
Smoker: Yes _____ No _____ How many per day? _____	
Site of implant placement: _____	
Immediate implant? Yes _____ No _____	
Native bone? Yes _____ No _____	
Single or multiple implants? _____	
Mucosal Thickness (millimeters) _____	
Bone Density (Hounsfield units) _____	
Complications with the surgical guide? Yes _____ No _____	
Other complications _____	

c. Timeline of study

Glosario de términos.

- 1. Computer-guided surgery (CGS)**
- 2. Cone beam computed tomography (CBCT).**
- 3. 3-Dimensional (3D)**
- 4. Hounsfield unit (HU).**
- 5. Full Mouth Plaque Score (FMPS).**

Investigador Principal [name]

Fdo: [name]

IP or tutor signature

Supporting researcher:

--	--

2.

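### Bone type and placement timing are structurally confounded by the eligibility rule, and the planned unadjusted T-tests do not separate them (Objectives 2 and 3)

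*Combined protocol and SAP*

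**What the plan says.** The inclusion criteria admit "Patients who need dental implant treatment without simultaneous regeneration". The specific objectives list two separate comparisons: "To assess the influence of time for implant placement (immediate or delay) on the accuracy of CGS" (Objective 2) and "To assess the influence of type of bone (native or regenerated bone" (Objective 3). Hypothesis 2 is an alternative hypothesis: "The time for implant placement (immediate or delay) has an influence on the accuracy of CGS". Bone type has no hypothesis of its own; Hypothesis 3 concerns mucosal thickness.

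Apart from descriptive statistics, the Statistical analysis section gives one sentence of method: "T-test and Pearson's linear correlation coefficient null test will be used to analyze the data". It mentions no restriction, stratification or multivariable model. The aim paragraph in the Introduction says that the listed factors will be considered in the analysis, but not how.

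The data collection form in the annex records whether the implant is immediate and, as a separate yes/no item ("Native bone? Yes"), whether the bone is native. No section defines immediate, delayed, native or regenerated.

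**The concern.** Two binary factors give four combinations, and the eligibility rule leaves one of them empty or nearly so. If no regeneration may take place at implant surgery, a regenerated site was treated at an earlier time. An immediate implant, in ordinary usage, is placed at extraction, so without simultaneous grafting it would normally sit in native bone. Three combinations remain: immediate in native bone, delayed in native bone, and delayed in regenerated bone.

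An all-sites T-test on bone type then compares a purely (or almost purely) delayed group with a mixed one. An all-sites T-test on timing compares a purely native group with a mixed one. If immediate placement is less accurate, native bone looks worse than it is, and a harmful effect of regenerated bone may be hidden or reversed. If regenerated bone is less accurate, the delayed group looks worse and the timing difference shrinks. Two of the four specific objectives are affected. The overlap follows from the entry criteria, so recruiting more patients would not remove it.

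**Working it through.** **The plan's own figure.** The only sample-size calculation is for a correlation, at "a 95% confidence level with Pearson's linear correlation coefficient null test". With the Fisher z formula, n = ((1.960 + z_power) / atanh(r))² + 3, two-sided 5%:
- r = 0.3 at 70 / 80 / 90% power: 67.42 / 84.93 / 112.68 (plan: 67 / 84 / 112).
- r = 0.5: 23.46 / 29.01 / 37.82 (plan: 23 / 29 / 37).

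The table reproduces when rounded down. The 84 is not in dispute, but it was set for the bone-density correlation and says nothing about the bone-type or timing contrasts.

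**Algebra.** Let τ be the effect of immediate placement on a deviation measure, β the effect of regenerated bone, q the share of native sites that are immediate, and p the share of delayed sites that are regenerated. With no immediate regenerated sites and additive effects:
- Objective 3, native minus regenerated, all sites: qτ − β. The target is −β, so the bias is qτ.
- Objective 2, immediate minus delayed, all sites: τ − pβ. The target is τ, so the bias is −pβ.

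**Illustration for Objective 3.** The documents give no group sizes, SD or timing effect, so these are assumptions: 84 independent sites, 28 regenerated and 56 native; SD 0.6 mm within each combination of timing and bone type; β = 0; two-sided 5% T-test. The all-sites standard error is 0.6 × √(1/28 + 1/56) = 0.139 mm. Rejection rates come from simulation, which allows for the extra spread in a native group made up of two means. For a tenth, 6 of 56 native sites were taken as immediate.

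| Native sites immediate | τ = 0.2 mm | τ = 0.3 mm | τ = 0.5 mm |
|---|---|---|---|
| Half: bias (mm) | 0.10 | 0.15 | 0.25 |
| Half: false-positive rate | 11% | 18% | 38% |
| A quarter: bias (mm) | 0.05 | 0.075 | 0.125 |
| A quarter: false-positive rate | 6% | 8% | 12–13% |
| A tenth: false-positive rate | 5% | 5% | 6% |

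A noncentral-t calculation that holds the SD at 0.6 mm in the mixed native group gives 11.0 / 18.7 / 42.8% for half immediate. The last figure is too high because it ignores that extra spread. Restricting the test to delayed sites gives about 5% in every scenario.

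**Masking.** With half of native sites immediate, τ = 0.3 mm and a true β = 0.3 mm in the same direction, the all-sites difference shrinks in size from 0.30 to 0.30 − 0.5 × 0.30 = 0.15 mm. The all-sites test detects the effect in about 17% of studies and the delayed-only test in about 45%.

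**Sensitivity to a partly filled cell.** If a share e of regenerated sites were immediate, the bias would be (q − e)τ. In SD units, with τ = 0.5 SD and q = 0.5, it falls from 0.25 at e = 0 to 0.225 at e = 5% and 0.20 at e = 10%. A few exceptions do not remove the problem.

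**The case against.** **The empty cell is inferred.** The protocol defines none of the terms, and no rule expressly bars an immediate implant at a site regenerated before extraction. A reader might infer that regenerated sites can only be delayed. The documents do not say so; almost all delayed is as far as ordinary meaning goes. This limits the certainty of the structure. The sensitivity check shows that it does not change the direction.

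**The comparator is not wrong in itself.** A reader might conclude that Objective 3 uses an invalid comparison group and that only delayed native sites can serve. That is too strong. With three filled combinations, an additive model with both factors estimates both effects. The defect is confounding built in by eligibility, with no adjustment planned.

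**Hypothesis 2 does not prove bias.** It gives neither direction nor size, and if timing has no effect the bias in Objective 3 is zero. This stands. The hypothesis shows only that the investigators expect an influence, so they cannot assume the bias away.

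**The general gap is univariable testing.** Location, bone density or mucosal thickness may also overlap with timing or bone type. That is true, but those overlaps depend on who enrols, whereas this one can be foreseen from the entry criteria.

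**Bone type looks like a lesser objective.** It has no hypothesis and did not drive the sample size. This tempers the severity, but timing has a hypothesis and is affected too.

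**Conclusion.** The point holds as structural confounding without planned adjustment. Followed as written, the Objective 2 and Objective 3 contrasts each carry part of the other factor's effect, to the extent that the other factor affects accuracy. It should be put right before the data are seen.

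The documents cannot fix the size. Under the stated assumptions, the false-positive rate for bone type runs from close to nominal (a tenth of native sites immediate) to about 38% (half immediate, 0.5 mm timing effect). These figures rest on the assumed 28/56 split, the 0.6 mm SD, additive effects and independent sites. The protocol allows up to four implants per patient, so independence is itself a simplification. The documents do not support saying that the Objective 3 result will be biased; they support saying that the plan offers no protection if timing matters.

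**What to change.** In the Statistical analysis section:
1. Define immediate, delayed, native and regenerated for analysis purposes, and report the two-by-two count of timing by bone type.
2. Compare native with regenerated bone among delayed implants only (Objective 3), and immediate with delayed among native-bone implants only (Objective 2 and Hypothesis 2). Delayed native sites are then the shared reference group. Present the all-sites comparisons as secondary.
3. An additive model containing both timing and bone type is an acceptable alternative. If the immediate-regenerated cell is empty, their interaction cannot be estimated, and the plan should say so. If patients contribute more than one implant, the model should also account for clustering within patient.

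**Cost.** Only protocol and analysis wording changes, because the data form already records both factors. The price is precision. With half of native sites immediate, Objective 3 becomes 28 versus 28, and the standard error rises from 0.139 to 0.6 × √(1/28 + 1/28) = 0.160 mm. Power for a 0.4 mm difference falls from 81% (all sites, no confounding) to 69%. With fewer immediate sites the loss is smaller: with a quarter immediate (28 versus 42) the standard error is 0.6 × √(1/28 + 1/42) = 0.146 mm.

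### The unit of analysis is not stated: a patient may receive up to four implants, but no rule picks one implant per patient and no patient term allows for several

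*Combined protocol and SAP*

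**What the plan says.** All references are to the combined protocol and SAP.

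- **Clinical procedures, implants per patient.** "Every patient could have a maximum of four implants to be placed (one per quadrant), in those cases, there will be one guide per implant". Four is a maximum. No distribution or mean is given.
- **Clinical procedures, outcomes.** All seven deviation measures are taken on an implant, for example "deviation at implant shoulder in millimeters; (3) tip: deviation at implant apex in millimeters".
- **Introduction, factors for analysis.** The list includes "1) Implant location (anterior or posterior); 2) Single or multiple implants; 3) Mucosal thickness; 4) Native or regenerated bone", followed by implant timing. Bone density is added in the specific objectives and hypotheses. All of these describe a site except single versus multiple, which describes the patient.
- **Specific objectives.** The first is "To assess the influence of implant location (anterior or posterior) on the accuracy of CGS", also a site-level question.
- **Sample size.** "To detect a weak magnitude correlation as significant, 84 patients will be needed for this study".
- **Statistical analysis.** Beyond descriptive statistics, the methods are "For a 95% confidence level and an estimated standard deviation, T-test" and, for Pearson's coefficient, "linear correlation coefficient null test will be used to analyze the data". The t-test is not said to be independent or paired, and no patient term is mentioned.
- **Contingency plan.** Exclusion is by patient: "if any of the data collected presents any error that could interfere in the data analysis, the patient will be excluded for the study".
- **Annex b, data collection.** Site, timing, bone type, mucosal thickness and bone density each have a single line under one patient number, below a heading for information gathered before surgery. There is no implant identifier.

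**The concern.** The plan does not say whether a row in the analysis is a patient or an implant, and the two readings leave different gaps.

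**One row per patient.** The t-test and Pearson test are then valid in form, but no rule says which of two, three or four implants supplies the deviation and the site factors.

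**One row per implant.** Implants in one mouth share a patient, a scan and an operator's session, so their deviations may be correlated. The named tests ignore this. The direction of the error depends on the factor: too many false positives when the factor tends to be alike within a mouth, about nominal when it is unrelated within a patient, and too few when its levels are contrasted within a mouth and the t-test is unpaired. The form of the t-test therefore matters under this reading.

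Every planned comparison depends on the answer.

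**Working it through.** **1. The plan's own figure.** Inputs from the sample size section: r = 0.3, 80% power, 95% confidence. Sidedness is not stated, but two-sided reproduces the table.

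n = ((1.960 + 0.842) / atanh(0.3))² + 3 = (2.802 / 0.3095)² + 3 = 84.9, against 84 stated.

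The other cells agree to rounding: 67.4 and 112.7 against 67 and 112; for r = 0.5, 23.5, 29.0 and 37.8 against 23, 29 and 37. One-sided gives 67.5 at 80% power and does not fit. Simulated power with 84 independent observations is 79.8%. So 84 is right for one independent observation per patient.

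**2. All implants as rows, bone-density test.** The documents give no ICC and no distribution of implants, so everything here is assumed. The variance inflation for a site-level covariate is approximately

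1 + (M − 1) × ICC(density) × ICC(outcome), with M = Σm² / Σm over patients with m implants,

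and the true error of a nominal 5% test is 2 × [1 − Φ(1.96 / √inflation)]. With both ICCs 0.5:

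| Shares with 1/2/3/4 implants | Mean | M | Inflation | True error |
|---|---|---|---|---|
| 70/15/10/5% | 1.5 | 3.0/1.5 = 2.0 | 1.25 | 8.0% |
| 25% each | 2.5 | 7.5/2.5 = 3.0 | 1.50 | 11.0% |
| half one, half four | 2.5 | 8.5/2.5 = 3.4 | 1.60 | 12.1% |

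Simulation with 84 patients, 20,000 replicates and outcome ICC 0.2 to 0.5 gives:

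- density unrelated within patient: 4.6–5.2%;
- density ICC 0.2: 5.5–6.3% (mean 1.5–1.8 implants), 5.9–8.0% (mean 2.5);
- density ICC 0.5: 6.0–8.6% (mean 1.5–1.8), 7.4–12.4% (mean 2.5).

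**3. All implants as rows, two-level factors.** For an independent t-test on a site factor present at 30% of sites (latent ICC 0.2–0.5), simulated error is 5.1–7.3% (mean 1.5–1.8) and 5.5–9.7% (mean 2.5). For single versus multiple it is 7.1–10.4% (mean 1.5), 6.0–8.1% (mean 1.8) and 5.5–8.6% (mean 2.5).

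**4. The opposite direction.** Take two implants per patient, one at each factor level, and an unpaired t-test. The true variance of the difference is (1 − ICC) times the assumed one, so the error is 2 × [1 − Φ(1.96 / √(1 − ICC))]: 2.8%, 1.9% and 0.6% at ICC 0.2, 0.3 and 0.5 (simulated 2.9%, 1.9%, 0.6%). Power for a 0.35 SD difference is 63%, 64% and 66%, against 70%, 76% and 88% if paired.

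**5. One implant per patient.** If the implant is chosen without regard to its deviation, single versus multiple has 4.4–5.3% error. The form's pre-surgical heading, and the measurement of mucosal thickness at planning, suggest the record is set before the postoperative CBCT.

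**6. The remedies.** Across bone density, a 30% site factor and single versus multiple (mean 1.5–2.5 implants, factor ICC 0.5, normal and skewed outcomes), simulated error is 4.3–5.9% with a random-intercept model and 4.3–5.5% with one implant per patient. Ordinary regression with cluster-robust errors gives 4.6–7.0%. Power for density at r = 0.3 is 92–99% with the mixed model and 78–82% with one implant.

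**The case against.** The best reply is that the plan already means one record per patient. The sample is counted in patients and reproduces for one observation each, the form has single entries under a patient number, and exclusions remove the patient. Under that reading, two-level factors are compared across patients, the t-test is independent, and the error rates in steps 2 to 4 do not arise. Much of this stands: the documents do lean that way. It does not close the gap, because a count of patients does not say which implant's deviation represents a patient with several. The form could also be filled in once per implant.

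It can also be said that the all-implants case is modest. That stands too. Values near 12% need both ICCs at 0.5 and half the patients with four implants, while the protocol gives four only as a maximum. A separate guide for each implant makes guide-fit error less shared, which may lower the correlation.

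A reader might infer that the recorded implant could be picked after its deviation is seen. In simulation, always recording the largest or smallest deviation gives 51–99.9% false positives for single versus multiple. The documents do not support this as a description of the plan: the site factors are listed under pre-surgical information, before any deviation exists. That is strong evidence rather than proof, since guide complications are recorded under the same heading and the form is undated. The figure is a worst case without textual support, for a factor that appears in no specific objective or hypothesis.

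**Conclusion.** The concern holds as a gap in specification. The outcomes and most factors are per implant, several implants per patient are allowed, the named tests need independent rows, and neither an index-implant rule nor a patient term is given.

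If all implants are analysed as independent, the density test's error lies between about 5% and about 12% under the assumed ICCs and a mean of 1.5 to 2.5 implants. Site-factor t-tests are mildly liberal when the factor is alike within a mouth, and an unpaired t-test is conservative when it splits within a mouth. Actual size and direction cannot be known from the documents. If one implant is fixed before deviations exist, error is near nominal.

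Two further inferences should be avoided. First, that 84 is wrong: it reproduces for one observation per patient. Second, that the density test would be safe even if implants were chosen by deviation: that holds only if density is unrelated to the number of implants. With density assumed 0.5 SD lower in multiple-implant patients, such a choice gives about 8–17% error.

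This should be fixed before deviations are measured. It does not undermine the design.

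**What to change.** State the unit of analysis in the statistical analysis section, and adopt one of two options.

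1. **All implants.** Replace the t-test and Pearson test with a linear mixed model with a random intercept for patient, entering single versus multiple as a patient-level factor. Check residuals for every outcome that is a magnitude (angle, base, tip, 3D offset). Cluster-robust errors can serve as a check, not as the main method.
2. **One implant per patient.** Keep the planned tests, naming the t-test as independent, on one implant chosen by a fixed rule, such as a random draw made before the postoperative CBCT is measured. This matches the 84-patient calculation.

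Under either option, record site, timing, bone type, mucosal thickness and density per implant under the patient number, and report the numbers of patients and implants.

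The cost is some wording, a few lines on the form and slightly more analysis work, with no extra patients, visits or scans. Under option 1, intervals for factors alike within a mouth may widen. Under option 2, the information from additional implants is lost.

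### Mucosal thickness follows one pre-operative rule that may not fit immediate sites, and no planned test accounts for timing, so a thickness correlation over all sites can reflect timing instead

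*Combined protocol and SAP*

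**What the plan says.** Under Clinical procedures, thickness is assessed while the implant is being planned: "in this step the assessment of the mucosal thickness will be performed using the STL and the DICOM files superimposed". One rule covers every site: "The measurement will be taken from the crestal bone until the soft tissue surface (mm").

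Clinical and study schedule, which is stated for all patients, gives a screening visit and then two study visits: "First visit: Data collection (intraoral scanning and CBCT acquiring") and "Second visit: Implant placement and post-operative CBCT". It lists no extraction visit and no planning scan after an extraction.

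Both timings are in scope. The overall objective concerns the "accuracy of computer-guided implant surgery on immediate and delayed implant placement". Hypothesis 2 reads "The time for implant placement (immediate or delay) has an influence on the accuracy of CGS", and hypothesis 3 reads "H0 The mucosal thickness does not have an influence on accuracy of CGS".

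The Statistical analysis section names descriptive statistics, a t-test and a Pearson correlation test. It mentions no adjustment or stratification and does not assign a test to each factor. The data collection form (annex b) has one thickness field for all cases and a separate yes/no field for immediate implants.

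**The concern.** The stated landmarks, bone crest and soft-tissue surface, describe a ridge covered by mucosa. If a tooth stands at the site when the scan is taken, it occupies the crest, and the protocol does not say where to measure. The evaluator could leave the field blank or choose another location.

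If another location is used, the recorded value may differ systematically between immediate and delayed sites. Timing is also expected to affect deviation. A correlation calculated over all sites would then combine any true thickness effect with the difference between the two timing groups. A timing effect could pass for a thickness effect, or could mask one. The result for hypothesis 3 could not be attributed to thickness, and collecting more sites would not cure that.

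**Working it through.** **1. The plan's own figure.** The sample size table uses a Pearson null test at 95% confidence. The Fisher z formula is n = ((z₀.₉₇₅ + z_power) / (atanh r + r/(2(n−1))))² + 3, two-sided. For r = 0.3 and 80% power it gives 83.98, rounded up to 84. The other five cells (67, 112, 23, 29, 37) also match. N = 84 is therefore not in question. It rests on correlations with bone density, not thickness.

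**2. Inputs.** n = 84 comes from the protocol; I take one site per patient. The documents do not give the following, so they are assumptions:
- share of immediate sites, p: 20-40%
- difference in mean recorded thickness between timings, dx: 0.5-2 within-group SD
- difference in mean deviation between timings, dy: 0.3-0.8 within-group SD
- no correlation between thickness and deviation within either timing group

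**3. Correlation produced by timing alone.** With q = p(1−p),

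r = q·dx·dy / √((1 + q·dx²)(1 + q·dy²)).

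- Low end (p = 0.2, dx = 0.5, dy = 0.3): q = 0.16, r = 0.024 / √(1.04 × 1.0144) = 0.023.
- Middle (p = 0.3, dx = 1, dy = 0.5): q = 0.21, r = 0.105 / √(1.21 × 1.0525) = 0.093.
- High end (p = 0.4, dx = 2, dy = 0.8): q = 0.24, r = 0.384 / √(1.96 × 1.1536) = 0.255.

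**4. False-positive rate of the nominal 5% test.** The test statistic has mean m = (atanh r + r/(2(n−1)))·√(n−3), and the rejection rate is Φ(m − 1.96) + Φ(−m − 1.96). At the high end, m = (0.2612 + 0.0015) × 9 = 2.36, which gives 66%.

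| p | dx | dy | r from timing | Unadjusted test rejects |
|---|---|---|---|---|
| 0.2 | 0.5 | 0.3 | 0.023 | about 6% |
| 0.2 | 1 | 0.5 | 0.073 | 10% |
| 0.3 | 1 | 0.5 | 0.093 | 13% |
| 0.3 | 1.5 | 0.5 | 0.127 | 21% |
| 0.4 | 2 | 0.8 | 0.255 | 66% |
| any | 0 | any | 0 | 5% |
| any | any | 0 | 0 | 5% |

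Simulation at n = 84 agreed with these rates to within about 2 percentage points. In the same simulations, a partial correlation given timing rejected in 4.7% to 5.3% of runs.

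**5. Masking.** Suppose timing does not affect deviation (dy = 0) but thickness is recorded differently. A true within-group r of 0.3 becomes 0.3 / √(1 + q·dx²). Over p = 0.2-0.4 this is 0.28-0.27 for dx = 1 and 0.23-0.21 for dx = 2. Power at n = 84 falls from 80% to 74-71% and to 58-50% respectively.

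**6. Using delayed sites only.** With 20%, 30% or 40% immediate, 67, 59 or 50 of 84 sites remain. Power for r = 0.3 is then 70%, 65% or 57%. The correlation detectable with 80% power rises from 0.30 to about 0.33, 0.36 or 0.38.

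**The case against.** The documents never mention extraction and never define immediate. The appointments are described as estimated, and the flow chart and timeline annexes, where the sequence might be shown, are not legible in the text available. That a tooth is present at scanning is therefore an inference, though a likely one. This stands.

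A reader might infer that the plan certainly mixes two different measurements. The documents do not support that. They leave the landmark at tooth-bearing sites unspecified. If the field is left blank there, a Pearson test on the available values would use delayed sites only, and nothing would be mixed. Blank values carry a different risk: the Contingency plan excludes a patient when a data error could interfere with the analysis, and it does not say whether an unmeasurable thickness counts.

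A reader might also infer that the plan commits to one Pearson correlation across all sites. It does not say so. Pooling is inferred from the single data field and from the absence of any adjusted or stratified analysis.

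Finally, a reader might extend the measurement fault to bone density. The protocol does not say where density is measured, so no such fault is shown.

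It is also fair to say that the quantified harm is ordinary confounding by timing, since adjustment brings the error rate back to about 5%. This stands, and it is why adjustment is the main remedy. Adjustment does not by itself make two differently taken measurements equivalent, so the landmark rule is still needed.

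**Conclusion.** The point holds in a limited form. As written, the plan leaves a thickness-accuracy correlation over all sites open to confounding by timing, and the measurement rule makes a difference in recorded thickness between timings plausible. The false-positive rate of about 6% to 66% rests wholly on the assumed share of immediate sites and the two assumed shifts. The documents fix neither the size nor the direction of the bias, and there is no inflation if either shift is zero.

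Thickness has its own hypothesis but is not among the specific objectives, and it does not drive N = 84. This is an inexpensive improvement that should be made, not a flaw that undermines the study.

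**What to change.** **Statistical analysis.** Test hypothesis 3 with the immediate/delayed variable in the model, by linear regression or partial correlation. Report the thickness relation separately for immediate and delayed sites, and give delayed sites only as a sensitivity analysis. Including timing in the bone-density model is sensible for the same general reason: it is a factor already collected and expected to matter.

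**Clinical procedures.** Define immediate placement. State which landmark is used when a tooth is present on the planning scan, or record thickness as not applicable there, and say that this does not exclude the patient. This must be settled before measurement starts.

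**Cost.** A few sentences and one extra model term; timing is already on the data form. Estimates within each timing group will be less precise. Keeping the delayed-only analysis as a sensitivity analysis avoids making the power loss in step 6 the price of the main test, and keeps the immediate sites that the overall objective covers, wherever a comparable value can be recorded.
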